11.1.1 Reporting Responsibilities

Reports of related and unexpected SAEs will be submitted to the Main REC within 15 days of the chief investigator becoming aware of the event, using the NRES template. The form will be completed in typescript and signed by the chief investigator so that the main REC can acknowledge receipt of safety reports within 30 days. A copy of the SAE notification and acknowledgement receipt will be sent to the R&D Directorate. Disease flare requiring treatment is an expected event and will not need to be reported as an SAE.

11.2 Trial Steering Committee (if applicable)

Not applicable. There will not be any data monitoring/steering/safety committees set up for this study.

11.3 Ethics & Regulatory Approvals

This protocol and related documents have been reviewed and approved by the Research Ethics Committee (_____).

12 Compliance and withdrawal

12.1 Subject compliance

No specific compliance testing will be carried out.

12.2 Withdrawal / dropout of subjects

Participants have the right to withdraw from the study at any time for any reason. The investigator also has the right to withdraw patients from the study drug in the event of intercurrent illness, AEs, SAE's, SUSAR's, protocol violations, cure, administrative reasons or other reasons. It is understood by all concerned that an excessive rate of withdrawals can render the study un-interpretable; therefore, unnecessary withdrawal of patients should be avoided. Should a patient decide to withdraw from the study, all efforts will be made to report the reason for withdrawal as thoroughly as possible. Because this is a non-interventional trial there won't be an interim analysis or premature termination of the study.

12.3 Protocol Compliance

Protocol violations will be documented on the protocol deviation log (in the trial master file) and reported by the chief investigator to the sponsor by email.

Guy's and St Thomas' NHS Foundation Trust

13 Data

13.1 Data to be collected

Data will be collected by the study investigators.

Data at the various time points include:

- Baseline:
 - Demographic data, disease extent history, concomitant medications, previous IBD medications, smoking history from patient history and notes.
 - Simple Clinical Colitis Activity Index (SCCAI), calculated by the assessor •
 - Serum CRP and albumin, and faecal calprotectin
 - Endoscopic Mayo Score, recorded by the endoscopist
 - Nancy histological index, reported by the pathologist •
 - STAT activation in peripheral blood mononuclear cells, recorded from • laboratory data
 - Cytokine expression in peripheral T cells, recorded from laboratory data
 - Gene and T/B cell receptor analysis in colonic biopsies, recorded from laboratory data
- Flare
 - Time point, alteration to treatment, faecal calprotectin, CRP, SCCAI, endoscopic Mavo score (if endoscopy performed), all recorded by the investigator from the patient notes.
 - Gene signatures in colonic biopsies, recorded from laboratory data
- Week 44
 - CRP, albumin, SCCAI, calprotectin, recorded from the patient's notes. •
 - Endoscopic Mayo score, recorded by the endoscopist
 - Nancy histological index, reported by the pathologist
 - STAT activation in peripheral blood mononuclear cells, recorded from laboratory data
 - Cytokine expression in peripheral T cells, recorded from laboratory data
 - Gene signatures in colonic biopsies, recorded from laboratory data

In the event of incomplete data, patients will be telephoned to arrange completion.

13.2 Data handling and record keeping

Pseudo-anonymised patient data will be kept on a password-locked computer. Every patient will be appointed a two-digit study number. All patient specific data will be recorded using only this number. The full name and birth date will only be recorded on the informed consent form. The study coordinator will monitor patient inclusion and protocol steps, coordinate data entry, perform data analyses and reporting. Data will be double entered into a Microsoft Excel spreadsheet to endure validity and quality.

All trial data will be stored in line with the Data Protection Act (1998). Records will be retained for a maximum of 7 years.

14 Statistical considerations

14.1 Sample size calculation (some pilot/feasibility studies may not require a formal sample size calculation)

Given the endpoints are exploratory, sample size calculations are not possible.

14.2 Statistical analysis

[name], clinical research fellow in gastroenterology, will perform the statistical analyses.

Baseline variables will be presented as either mean and standard deviation or medians and inter quartile range, depending on the normality of the data.

Receiver operator curves will be generated to determine optimal cut-offs for continues variables, predictive of disease flare.

Kaplan-Meier curves will be generated to allow comparisons of subdivisions of patients based on genetic and biochemical variables, using determined cut-offs.

Univariate and Multivariate analyses will be performed on clinical, biochemical and genetic variables to establish predictors of disease flare.

15 Ethical considerations

This is a non-interventional, observational study. Approvals will be sought from REC and HRA. Patients will need to provide informed consent to participate, and the only data collected from patients which occur in addition to standard of care are the additional tissue and blood samples collected at baseline and at week 44 for genetic, immune cell and cytokine analyses. Decisions regarding patient's care will have no relation to the study and will be directed by the patient's care team. Data collection and monitoring will occur in accordance with the rules and regulations set out above. The study design, management, undertaking, analysis and dissemination of results have had patient involvement, via a patient representative who sits on our project approvals board.

16 Financing and Insurance

Guy's and St Thomas' NHS Foundation Trust will take primary responsibility for ensuring that the design of the study meets appropriate standards and that arrangements are in place to ensure appropriate conduct and reporting are adhered to. King's College London as co-sponsor also provides cover under its No Fault Compensation Insurance, which provides for payment of damages or compensation in respect of any claim made by a research subject for bodily injury arising out of participation in a clinical trial or healthy volunteer study (with certain restrictions).

17 Reporting and dissemination

It is intended that the results of the study will be reported and disseminated at international conferences and in peer-reviewed scientific journals. A manuscript of the final study results will be submitted to an IBD specific journal (IBD or JCC) or to the IBD section of a general gastroenterology journal (Gut, Gastroenterology or CGH).

18 Useful reading/websites

Integrated Research Application System (IRAS) https://www.myresearchproject.org.uk/ Health Research Authority (HRA) www.hra.nhs.uk

HRA Guidance for Patient Information Sheet and Informed Consent http://www.hra.nhs.uk/research-community/before-you-apply/participant-information-sheets-and-informed-consent/

CONSORT statement A set of recommendations for improving the quality of reports of parallel group randomised trials http://www.consort-statement.org/

ICH Harmonised Tripartite Guidelines for Good Clinical Practice (1996) http://www.ich.org/fileadmin/Public Web Site/ICH Products/Guidelines/Efficacy/E6/E6 R1 Guideline.pdf

Martin Bland et al, Statistical guide for research grant applications http://www-users.york.ac.uk/~mb55/guide/guide.htm Includes detailed information and definitions of many aspects required for a research protocol as well as information about randomisation software and services

Martin Bland, Directory of randomisation software and services http://www-users.york.ac.uk/~mb55/guide/randsery.htm

Declaration of Helsinki (http://www.wma.net/en/30publications/10policies/b3/index.html)

Guy's and St Thomas' NHS

NHS Foundation Trust

19 Appendix 1 – Information with regards to Safety Reporting in Non-CTIMP Research

	Who	When	How	To Whom
SAE	Chief Investigator	-Report to Sponsor within 24 hours of learning of the event -Report to the MREC within 15 days of learning of the event	SAE Report form for Non- CTIMPs, available from NRES website.	Sponsor and MREC
Urgent Safety Measures	Chief Investigator	Contact the Sponsor and MREC Immediately	By phone	Main REC and Sponsor
		Within 3 days	Substantial amendment form giving notice in writing setting out the reasons for the urgent safety measures and the plan for future action.	Main REC with a copy also sent to the sponsor. The MREC will acknowledge this within 30 days of receipt.
Progress Reports	Chief Investigator	Annually (starting 12 months after the date of favourable opinion)	Annual Progress Report Form (non-CTIMPs) available from the NRES website	Main REC
Declaration of the conclusion or early termination of the study	Chief Investigator	Within 90 days (conclusion) Within 15 days (early termination) The end of study should be defined in the protocol	End of Study Declaration form available from the NRES website	Main REC with a copy to be sent to the sponsor

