	dose commencing on maintenance tofacitinib therapy.
Primary objective	To identify biochemical and genetic markers predictive of
	ulcerative colitis flare
Secondary objective (s)	To identify clinical and disease characteristics predictive
	of ulcerative colitis flare
Number of Subjects/Patients	50 patients
Trial Design	Prospective observational study
Endpoints	1. Flare requiring drug discontinuation, surgery
	(colectomy) or addition of new therapy for ulcerative
	colitis.
	2. Endoscopic activity at week 44 endoscopy
Main Inclusion Criteria	Ulcerative colitis patients commencing tofacitinib
	maintenance dosing, undergoing endoscopy as part of
	their routine clinical care.
Statistical Methodology and Analysis	Receiver operator curves will be generated to determine
	optimal cut-offs for continues variables, predictive of
	disease flare.
	Kaplan-Meier curves will be generated to allow
	comparisons of subdivisions of patients based on genetic
	and biochemical variables, using determined cut-offs.
	Univariate and Multivariate analyses will be performed on
	clinical, biochemical and genetic variables to establish
	predictors of disease flare.

5 Introduction

Tofacitinib has been shown in large-scale randomised clinical trials to be an effective treatment for patients with moderate to severe UC that is resistant to both conventional treatment and to biologic therapy¹. In the few months it has been available in the UK, our unit has accrued some of the biggest experience in the country. Our initial experience and prospectively collected observational data suggest that the drug performs at least as well as clinical trial results would indicate.

Results from the OCTAVE clinical trial program led to the approval of an induction regimen of 10mg BD, with subsequent dose reduction in responders to 5mg BD after at least 8 weeks. This maintenance regimen was shown to maintain remission with greater efficacy than placebo¹. However, the clinical trial data further suggests that in patients who have previously failed anti-TNF therapy, the 10mg BD maintenance dose is superior to the 5mg BD dosing¹. Anecdotally, many clinicians are accordingly favouring continuing the 10mg bd dose in higher risk patients (biologic failures) for up to 52 weeks, rather than dropping to the maintenance dose at week 8.

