7.1 Study Design

This is a prospective observational study. We will prospectively enroll a cohort of 50 UC patients who have achieved an adequate response to tofacitinib at a dose of 10mg bd and whose dose is being reduced to 5mg bd following a routine flexible sigmoidoscopy. Colonic

tissue and blood samples will be collected at study entry, and patients' disease course will be followed-up through routine care.

Week 44 has been chosen for the primary endpoint, as 44 weeks post dose de-escalation was used as the endpoint in OCTAVE Sustain.

Primary endpoint:

• Biomarkers, clinical markers and histological markers associated with ongoing treatment with 5mg bd in the absence of steroids at week 44.

Secondary Endpoints

• Biomarkers, clinical markers and histological markers associated with steroid free endoscopic remission at routine endoscopy at week 44

Biomarkers / outcome measures will include:

- Clinical status (SCCAI)
- CRP and faecal calprotectin (as part of routine care)
- Histological markers of disease activity (Nancy histological index) (as part of routine care)
- STAT activation in peripheral blood mononuclear cells
- Cytokine expression in peripheral T cells
- Gene signatures in colonic biopsies

Guy's and St Thomas' MHS

NHS Foundation Trust

Flow Diagram

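### Section 14.2 analyses flare, but the Section 7.1 primary endpoint is steroid-free persistence on 5 mg bd; a drug stop without flare fails one and is no event in the other

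*Protocol*

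**What the plan says.** Four places in the Protocol define or use the outcome.

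- **Section 7.1 (primary endpoint):** markers associated with "ongoing treatment with 5mg bd in the absence of steroids at week 44".
- **Section 4 (synopsis, endpoint 1):** "Flare requiring drug discontinuation, surgery" (colectomy) or the addition of a new therapy for ulcerative colitis.
- **Section 9.3 (visit schedule):** the flare visit is labelled with an SCCAI of 5 or more. No change of treatment is needed.
- **Section 14.2 (analysis):** the ROC step is "Receiver operator curves will be generated to determine optimal cut-offs for continues variables, predictive of disease flare". The next step is "Kaplan-Meier curves will be generated to allow comparisons of subdivisions of patients based on genetic and biochemical variables, using determined cut-offs". The last is "Univariate and Multivariate analyses will be performed on clinical, biochemical and genetic variables to establish predictors of disease flare".

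Section 12.2 foresees two kinds of early exit. One is leaving the study: "Participants have the right to withdraw from the study at any time for any reason". The other is the investigator taking a patient off the drug for intercurrent illness, adverse events or other reasons. Section 9.3 gives the week 44 assessment to patients still on tofacitinib. Section 13.1 lists treatment alteration as a data item only under flare.

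**The concern.** The analysis section and the primary endpoint do not share an outcome. The ROC and the regressions are built on flare, and the Kaplan-Meier groups inherit the ROC cut-offs. Nothing in 14.2 is directed at steroid-free persistence on 5 mg bd. Followed as it stands, the section leaves the primary endpoint without an analysis and chooses cut-offs on something else.

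The patients on whom the outcomes disagree are ones the Protocol expects: those who stop for an adverse event or intercurrent illness without a flare. The study exists to find predictors in 50 patients, so the classification of a handful can change which markers look predictive and where a cut-off falls. The three definitions of flare add a second layer, because the event in 14.2 could be any of them.

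**Working it through.** The Protocol states no event rate, dropout rate, alpha or power, so there is no figure of its own to reproduce. The check has two parts.

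**1. The same patient under each definition**

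| Patient | 7.1: on 5 mg bd, steroid-free at week 44 | Synopsis: flare needing stop, colectomy or new therapy | 9.3: SCCAI of 5 or more |
|---|---|---|---|
| Stops drug for an adverse event, never flares | Fails | No event | No event |
| SCCAI reaches 5, settles with no treatment change, still on 5 mg bd and off steroids at week 44 | Meets | No event | Event |
| Flares, a new therapy is added, still on 5 mg bd and off steroids at week 44 | Meets | Event | Event, if SCCAI was 5 or more |
| Leaves the study unflared, may still be taking the drug | Unknown | Unknown after exit | Unknown after exit |

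The first row is the clear case: a failure under 7.1, and no event under either flare definition. The next two rows show disagreement in the other direction.

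**2. Illustration of size (all rates are assumptions)**

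*Event proportion.* Let F be the 44-week flare risk without stops and W the 44-week risk of a non-flare stop, independent of flare. If stops count as failures, the event proportion is 1 − (1 − F)(1 − W). If they count as non-flare, it is the observed flare proportion, taken here from a simulation (400,000 patients per scenario, exponential times, flare hazard ratio 2 per SD of the marker).

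- F = 0.50, W = 0.05: 1 − 0.50 × 0.95 = 52.5% as failures; 48.9% as non-flare. Gap 3.6 points, or 0.036 × 50 = 1.8 patients.
- F = 0.30, W = 0.20: 1 − 0.70 × 0.80 = 44% (simulated 43.9%) as failures; 27.1% as non-flare. Gap 16.8 points, or 0.168 × 50 = 8.4 patients.

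These are the extremes over F of 30 to 50% and W of 5 to 20%.

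*AUC.* Separate simulation with 300,000 patients, F = 30%, and a flare hazard ratio of 2.2 per SD. The AUC for flare with complete follow-up is 0.74. Values are for W = 10/20/30%.

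| Relation of stops to the marker | Stops as failures | Stops as non-flare |
|---|---|---|
| Independent | 0.69 / 0.66 / 0.64 | about 0.73 throughout |
| Log hazard 0.5 per SD | 0.73 / 0.72 / 0.72 | 0.72 / 0.71 / 0.70 |

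With independent stops, failure coding costs 0.74 − 0.69 = 0.05 up to 0.74 − 0.64 = 0.10. With marker-related stops it costs 0.01 to 0.02, and non-flare coding costs 0.02 to 0.04.

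*Precision at n = 50.* Hanley-McNeil with A = 0.74, 15 flares and 35 non-flares:

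- A/(2 − A) = 0.587; 2A²/(1 + A) = 0.629; A² = 0.548.
- Variance = [0.74 × 0.26 + 14 × (0.5873 − 0.5476) + 34 × (0.6294 − 0.5476)] / (15 × 35) = (0.192 + 0.556 + 2.782) / 525 = 0.0067.
- Standard error = 0.08.

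**The case against.** **The analysis matches the objective.** Section 6 makes flare the target of the primary objective, so 14.2 is not aimed at a stray outcome. That is true, and it locates the conflict between the objective and analysis on one side and the 7.1 endpoint on the other. It does not remove it.

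**Handling of censoring belongs in an analysis plan.** This also stands. A reader might infer that the Protocol commits to an ordinary ROC that labels early exits as non-flare, to a Kaplan-Meier analysis that censors them, and to a primary endpoint that fails them, so that one patient is coded three ways. The text does not say so. Section 14.2 names no type of ROC, no Kaplan-Meier event and no censoring rule. The three-way coding is possible and nothing prevents it, but it is not prescribed. Choosing between conflicting protocol outcomes, however, is more than an analysis plan should have to settle.

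**Withdrawals are not all failures.** Correct. Someone who leaves the study may still be on 5 mg bd, so week 44 status is unknown. Only the drug stop is a failure under 7.1.

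**Kaplan-Meier is not shown to overstate risk.** A reader might note that, with 20% independent stops, one minus Kaplan-Meier gives 30% while about 27% are seen to flare. The 30% is the simulated flare risk without stops; 27% is the crude incidence in the presence of stops. These are different estimands. Section 14.2 uses the curves to compare groups, which is legitimate with other stops censored.

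**The AUC shifts are small against the noise.** Under non-flare coding they are, with a standard error of 0.08. Under failure coding with independent stops they are of the same order as the standard error. They reflect a changed target, not sampling error, so precision does not excuse them.

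**Conclusion.** The concern holds as a conflict of outcomes that should be resolved before analysis. Sections 4, 7.1, 9.3 and 14.2 use outcomes that classify the same patient differently, and no analysis in 14.2 addresses the 7.1 primary endpoint. This rests on the text alone.

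The size is illustrative. It depends on assumed flare rates, stop rates, marker strength and the relation of stops to the marker, none of which the Protocol gives. Within those assumptions, swapping flare for persistence matters more than the choice between ROC and Kaplan-Meier handling when stops are independent of the marker. When stops are related to it, the two codings give similar AUCs. The illustration does not support a claim that the planned AUC will be wrong by a given amount, or that the ROC and Kaplan-Meier methods are themselves unsuitable.

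**What to change.** 1. Reconcile Sections 4, 7.1, 9.3 and 14.2 to one primary outcome, and say whether the SCCAI threshold defines the event or only triggers the flare visit. The choice is for the investigators.
2. State how a non-flare drug stop counts: as a failure if the outcome is persistence, or as censored or competing if the outcome is flare. State separately how a study withdrawal with unknown week 44 status counts.
3. Use that event coding in the ROC, Kaplan-Meier and regression analyses. If a second outcome is kept, give it its own named analysis.
4. Add to Section 13.1 the date and reason of every drug stop, whether or not there was a flare.

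A time-dependent ROC and cumulative incidence curves are optional sensitivity analyses. In an exploratory study of 50 patients they are not needed to cure the conflict.

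The cost is wording changes, possibly including the primary endpoint itself, and a little extra coding from the notes. No visits, samples or patients are added.

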For genetic studies, RNA will be prepared using Qiaprep microRNA kit, then quantified on a Qubit instrument and 2ug RNA will be sent for library preparation and RNA-sequencing using commercial genomic services at Novogene. Briefly, mRNA is purified from total RNA using poly-T oligo-attached magnetic beads, then isolated mRNA is fragmented, reverse transcribed and stranded libraries will be prepared and sequenced using the Illumina platform to generate at least 20M reads per sample. Bioinformatic analysis of the RNA sequencing data will be carried out at Novogene as part of the service package and will provide comprehensive gene expression analysis. Unsupervised and supervised clustering analysis will be performed to provide a high-level view of the differences between the two groups analysed and to produce a differential gene expression (DEG) list. Enrichment analysis of the DEGs will be performed using the clusterProfiler software for enrichment analysis, including GO Enrichment, DO Enrichment, KEGG and Reactome database, to predict biological functions or pathways are significantly associated with DEGs. The top 5-10 genes from the DEG list will be validated by quantitative real-time PCR using RNA from mucosal tissue and also from PBMC and T cells isolated from peripheral blood. In addition, obtained biopsies will be defrosted and processed either by:

- 1. A whole tissue digestion protocol
- Placed in culture to allow crawl out of lymphocytes as previous described (Di Marco Barros Cell 2016)
- 3.

The resulting single cell suspension will either be analysed by flow cytometry (in the presence/absence of stimulation) or processed for transcriptomic analysis. Further, a single biopsy will be placed into RNAlater and subsequent RNA/DNA extraction performed. The resulting material will be saved for genotyping, gene expression analysis and T/B cell receptor analysis.

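### Cut-offs optimised by ROC against flare are then compared by Kaplan-Meier in the same 50 patients, so the apparent separation is biased upward

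*Protocol*

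**What the plan says.** Section 14.2 lists three analyses of the markers, without ranking them.

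- Cut-off selection: "Receiver operator curves will be generated to determine optimal cut-offs for continues variables, predictive of disease flare".
- Comparison of the resulting groups: "Kaplan-Meier curves will be generated to allow comparisons of subdivisions of patients based on genetic and biochemical variables, using determined cut-offs".
- Regression: "Univariate and Multivariate analyses will be performed on clinical, biochemical and genetic variables to establish predictors of disease flare".

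The statistical row of the synopsis (section 4) gives the same sequence, beginning "Receiver operator curves will be generated to determine".

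There is a single data set. Section 7.1 states: "We will prospectively enroll a cohort of 50 UC patients". The same section sets the time horizon: "Week 44 has been chosen for the primary endpoint, as 44 weeks post dose de-escalation was used as the endpoint in OCTAVE Sustain". Section 14.1 gives no sample size calculation: "Given the endpoints are exploratory, sample size calculations are not possible".

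The only validation described is in section 10.3: "The top 5-10 genes from the DEG list will be validated by quantitative real-time PCR using RNA from mucosal tissue". That is a laboratory check of a measured expression level, not a test of a cut-off in other patients.

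**The concern.** An ROC-optimal cut-off is the threshold at which flaring and non-flaring patients look most different. With 50 distinct marker values there are 50 − 1 = 49 candidate thresholds, and the plan keeps the best. Splitting the same patients there and comparing their flare curves uses the outcome twice. An ordinary p-value treats the split as if it had been given beforehand, which it was not.

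The accuracy figures have the same problem. A null marker has true sensitivity + specificity − 1 equal to 0 at every threshold. The largest of 49 noisy estimates of zero will usually be above zero.

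At stake is the credibility of any threshold the study publishes. The introduction and section 6 say that such markers should eventually help decide which patients stay on the higher dose. A threshold and hazard ratio obtained this way would look better than they are and would tend to shrink or disappear on replication.

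**Working it through.** The protocol states no error rate, power or flare rate, so there is no figure to reproduce. The size of the bias was found by simulating the planned sequence with a marker unrelated to flare.

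**Inputs from the protocol:** n = 50 (section 7.1); follow-up 44 weeks (section 7.1); ROC cut-off against flare, then a Kaplan-Meier comparison at that cut-off (section 14.2).

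**Assumptions, because the protocol gives no figure:**
- Probability p of flare by week 44: 20% to 60%.
- Comparison of curves: two-sided log-rank test at 5%.
- Meaning of optimal: Youden or closest-to-corner.
- Direction (high or low values mean risk): fixed in advance or taken from the data.

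**Steps, 4,000 runs per setting:**
1. Draw 50 marker values independent of outcome. Draw exponential flare times with weekly hazard λ = −ln(1 − p)/44 and censor at week 44. For p = 40%, λ = 0.5108/44 = 0.0116.
2. At each threshold compute sensitivity and specificity against flare yes/no. Youden maximises J = sensitivity + specificity − 1. Closest-to-corner minimises (1 − sensitivity)² + (1 − specificity)². With free direction, Youden maximises |J|, and closest-to-corner takes its direction from whether the AUC is above or below 0.5.
3. Split the same 50 patients there and compute the log-rank statistic (Σ(O − E))²/ΣV. Count it as significant above 3.841.
4. As a control, split at the median, which ignores the outcome.

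**False-positive rate for a null marker (nominal 5%):**

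| Flare by week 44 | Corner, fixed | Corner, free | Youden, fixed | Youden, free | Median split |
|---|---|---|---|---|---|
| 20% | 12.5% | 23.3% | 20.3% | 34.2% | 5.2% |
| 30% | 10.5% | 20.2% | 20.2% | 35.2% | 4.7% |
| 40% | 9.9% | 20.8% | 19.9% | 36.6% | 4.8% |
| 50% | 10.2% | 18.7% | 20.3% | 34.3% | 5.0% |
| 60% | 9.2% | 19.5% | 19.2% | 34.5% | 5.5% |

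The Monte Carlo standard error is √(0.20 × 0.80/4,000) = 0.6 percentage points at a rate of 20%, and √(0.05 × 0.95/4,000) = 0.3 points at 5%.

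**Sensitivity checks:**
- At least 5 patients per group: Youden gives 17–19% (fixed) and 32–35% (free).
- At least 10 per group: Youden with free direction gives 26–28%.
- 20% dropout at a 40% flare rate: 20% (Youden, fixed), 34% (Youden, free), 11% (corner, fixed).

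The flare rate hardly matters. The criterion and the direction do. The control returns the nominal 5%, so the excess comes from the cut-off search.

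**Effect size:** under Youden with free direction and flare in 30–50%, the median apparent hazard ratio for a null marker is 2.2–2.8, where the truth is 1.

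**Which columns apply:** the introduction hypothesises increased STAT activation, so the fixed-direction columns fit STAT markers if that direction is used. For cytokines it speaks only of changes, and for genes only of possible signatures. The free-direction columns are the relevant ones there.

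**The case against.** The strongest reply is that the study is exploratory and says so in section 14.1. It claims no error rate, and section 15 keeps patient care independent of the study, so no participant is affected. Internal validation and choice of test often belong in a statistical analysis plan, which is not shown and might supply them. This lowers the severity but does not remove the bias. The protocol itself fixes the sequence, and a plan that followed it without correction would inherit the problem. Hazard ratio, sensitivity and specificity at the cut-off are inflated whether or not a p-value is reported.

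Some stronger readings are tempting but not supported:

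- **A single unconditional error rate.** A reader might quote 17–36% as the false-positive rate. That holds only for the Youden rule with a log-rank test at 5%, none of which the protocol names. Closest-to-corner is an equally ordinary reading of optimal and starts at about 9%.
- **The main analysis of the primary objective.** Section 14.2 gives no ranking. The analysis said to establish predictors is the regression, and nothing says it uses dichotomised markers. Gene discovery has its own route in section 10.3.
- **A censoring mismatch.** A reader might infer that patients lost before week 44 count as flare-free in the ROC step and as censored in the Kaplan-Meier step. The protocol does not say how they enter the ROC, and such handling can be left to the analysis plan.
- **A total count of false findings.** The protocol fixes no number of markers to be split, so the per-marker rate cannot be turned into an expected count.

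**Conclusion.** The procedure in section 14.2 and the synopsis is circular as written, and the results at the optimised cut-offs will be too favourable. The per-marker false-positive rate is roughly two to seven times nominal: 9/5 = 1.8 at the low end and 37/5 = 7.4 at the high end. The range runs from about 9–13% (closest-to-corner, direction fixed) to about 33–37% (Youden, direction from the data). It rests on an assumed log-rank test at 5%, an assumed flare rate of 20–60%, and no minimum group size. It does not include the further selection that arises when genes are first picked by comparing relapsers with non-relapsers in the same patients.

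This should be fixed before the analysis is run. Given the exploratory endpoints, and since the regressions can be done without the cut-offs, it does not undermine the study as a whole.

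**What to change.** Change section 14.2 and the statistical row of the synopsis as follows.

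1. Base inference on the univariate and multivariate analyses already planned, with each continuous marker kept continuous.
2. Present Kaplan-Meier curves split at the median, or at a cut-off fixed and recorded before outcome data are seen.
3. If an ROC-optimised cut-off is shown, label it as hypothesis-generating. Report bootstrap optimism-corrected sensitivity and specificity. Replace the naive log-rank p-value with a permutation p-value that repeats the whole cut-off search, including the choice of direction where that is left to the data.

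The flare outcome must be the same in all of these steps. The synopsis, section 7.1 and section 9.3 describe flare or treatment failure differently, so the text should say which description the analyses use.

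The cost is a few sentences and a little more analysis code, with no new data or samples. The downside is that reported effects will be smaller and fewer splits will look significant.
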